7.8. Concomitant Therapy and Supportive Care

7.8.1. Olaratumab Infusion-Related Reactions

As with other monoclonal antibodies, hypersensitivity reactions may occur during or following olaratumab administration.

A 1-hour observation period is required after the administration of olaratumab in the first and second cycles. If there is no evidence of an IRR during the initial 2 cycles of olaratumab, then no observation period is required for subsequent treatment cycles. In the event that a Grade 1 or 2 IRR occurs after Cycle 2, the 1-hour observation period will be reinstated for a minimum of 2 cycles. The reinstated observation period may be suspended after 2 cycles if the patient shows no further signs or symptoms of an IRR. During the observation period, patients treated with olaratumab should be closely monitored for signs and symptoms indicative of an IRR by the medical staff from the start of the infusion until at least 1 hour after the end of the infusion in an area where emergency medical resuscitation equipment and other agents (epinephrine, prednisolone equivalents, etc.) are available.

Treatment guidelines for olaratumab IRRs as well as premedications for subsequent infusions are described in [Table JGDR.15](#).

Olaratumab infusion reactions will be defined according to the NCI-CTCAE Version 4.0 definition of IRRs.

Symptoms occurring during or following infusion of investigational therapy may also be defined according to AE categories such as allergic reaction, anaphylaxis, or cytokine release syndrome (NCI-CTCAE Version 4.0 Section “Immune system disorders”). In the setting of symptoms occurring during or following infusion of investigational therapy, investigators are encouraged to

use the AE term “infusion-related reaction” and any additional terms (including those not listed here) that best describe the event.

Table JGDR.15. Olaratumab Infusion-Related Reaction Treatment Guidelines

NCI CTCAE Grade	Treatment	Premedication at Subsequent Infusions

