9.2.3. Adverse Events of Special Interest

Adverse events of special interest (AESI) are events that have been identified as safety signals during preclinical or early clinical trials or based on class effects of similar drugs. These events will be monitored prospectively in the clinical developmental program. Each event is defined by a careful assessment and grouping of individual related Medical Dictionary for Regulatory Activities (MedDRA) preferred terms.

The following events will be considered as AESI for the combination of olaratumab and doxorubicin, ifosfamide and mesna:

- infusion-related reactions
- cardiac arrhythmias and cardiac dysfunction
- encephalopathy
- renal toxicity

Refer to Section 7.8.1 for treatment considerations relative to the occurrence of olaratumab IRRs. Refer to Section 7.4 for treatment considerations relative to dose delays, modifications and discontinuations from doxorubicin, including AEs of concern or AESI.

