10.3.6. Immunogenicity Analyses

Incidence of treatment-emergent anti-olaratumab antibodies will be tabulated. The potential impact of immunogenicity on olaratumab exposure will be evaluated in the population PK modeling exercises where immunogenicity will be evaluated as a covariate. In addition, graphical assessments will be conducted, as appropriate, to compare drug exposure between treatment-emergent antidrug antibody (ADA)-negative and treatment-emergent-ADA-positive patients at correspondent visits, or before and after treatment-emergent-ADA development for patients who developed treatment-emergent-ADA.

In the event of an IRR, the immunogenicity and olaratumab serum concentrations will be tabulated.

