5.8.3. Adverse Events

Adverse event (AE) severity grades will be assigned by the investigator using Common Terminology Criteria for Adverse Events (CTCAE) Version 4. AE verbatim text will be mapped by the sponsor or designee to corresponding terminology within MedDRA.

Pre-existing conditions are defined as any AEs that begin prior to the first dose of study drug.

Treatment-emergent adverse event (TEAE) are defined as any AE that occurred or worsened between the day of first dose and up to 30-day follow-up visit (or up to any time if serious and related to study treatment).

Comparisons of pre-existing conditions to on-treatment events at the low level term (LLT) level will be used in the treatment-emergent computation.

The following AE will be considered as **AE of special interest (AESI)** for the combination of olaratumab and doxorubicin, ifosfamide and mesna: infusion-related reactions (IRR), cardiac arrhythmias, cardiac dysfunction, encephalopathy, renal toxicity. PT for AESI are listed in [Appendix 1](#). Categories of AESI may be modified as the understanding of the safety of the investigational drug increases. The final list of categories will be reported in the clinical study report (CSR).

Consolidated AE will include Abdominal Pain, Anemia, Fatigue, Hyperbilirubinaemia, Hypertension, Hypoalbuminaemia, Hypokalaemia, Hypomagnesaemia, Hyponatraemia, Hypoproteinemia, Intestinal Obstruction, Leukocytosis, Leukopenia, Lymphopenia, Mucositis, Neuropathy, neutropenia, Musculoskeletal pain, Rash, and Thrombocytopenia. Each consolidated AE contains PTs identified as clinically identical or synonymous. PT for consolidated AEs are listed in [Appendix 2](#).

The following summaries and listings will be produced:

- Overview of AE
- Summary of TEAE by PT (any grade and Grade ≥ 3)
- Summary of DLT
- Summary of DET
- Summary of TEAE by system organ class (SOC) and PT (any grade and Grade ≥ 3)
- Summary of TEAE by SOC and PT and maximum grade (1-5)
- Summary of treatment-emergent serious AE (SAE) by SOC and PT (any grade and Grade ≥ 3)
- Summary of AEs as reason for study treatment discontinuation by SOC and PT
- Summary of and listing of TEAE leading to dose delays, omissions, interruptions, reductions, treatment discontinuation, hospitalizations, transfusions

- Summary of treatment-emergent AESI (any grade and Grade ≥ 3)
- Summary of treatment-emergent consolidated AE (any grade and Grade ≥ 3)
- Listings of DLT, DET, SAE, TEAE, AESI

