Loss of consciousness
Palpitations
Rebound tachycardia
Sudden death
Syncope
Tachycardia
Tachycardia paroxysmal
Bradycardia
Ventricular asystole
Accessory cardiac pathway
Adams-Stokes syndrome
Agonal rhythm
Atrial conduction time prolongation
Atrioventricular block
Atrioventricular block complete
Atrioventricular block first degree
Atrioventricular block second degree
Atrioventricular conduction time shortened
Atrioventricular dissociation
Bifascicular block
Brugada syndrome
Bundle branch block
Bundle branch block bilateral
Bundle branch block left
Bundle branch block right
Conduction disorder
Defect conduction intraventricular
Electrocardiogram delta waves abnormal
Electrocardiogram PQ interval prolonged
Electrocardiogram PQ interval shortened
Electrocardiogram PR prolongation
Electrocardiogram PR shortened
Electrocardiogram QRS complex prolonged
Electrocardiogram QT prolonged
Electrocardiogram repolarisation abnormality
Lenegre's disease
Long QT syndrome
Sinoatrial block
Trifascicular block
Ventricular dyssynchrony
Wolff-Parkinson-White syndrome

AESI

Preferred Term

Nodal arrhythmia
Nodal rhythm
Sick sinus syndrome
Sinus arrest
Sinus arrhythmia
Sinus bradycardia
Wandering pacemaker
Arrhythmia
Heart alternation
Heart rate irregular
Pacemaker generated arrhythmia
Pacemaker syndrome
Paroxysmal arrhythmia
Pulseless electrical activity
Reperfusion arrhythmia
Withdrawal arrhythmia
Arrhythmia supraventricular
Atrial fibrillation
Atrial flutter
Atrial parasystole
Atrial tachycardia
Junctional ectopic tachycardia
Sinus tachycardia
Supraventricular extrasystoles
Supraventricular tachyarrhythmia
Supraventricular tachycardia
ECG P wave inverted
Electrocardiogram P wave abnormal
Retrograde p-waves
Anomalous atrioventricular excitation
Cardiac flutter
Extrasystoles
Tachyarrhythmia
Accelerated idioventricular rhythm
Cardiac fibrillation
Parasystole
Rhythm idioventricular
Torsade de pointes
Ventricular arrhythmia
Ventricular extrasystoles
Ventricular fibrillation
Ventricular flutter
Ventricular parasystole
Ventricular pre-excitation
Ventricular tachyarrhythmia

AESI

Encephalopathy

Preferred Term

Ventricular tachycardia

Blurred vision

Coma

Confusion

Extrapyramidal symptoms

Hallucinations

Psychotic behavior

Seizures

Somnolence

Urinary incontinence

Infusion-related Reactions

Allergic oedema

Anaphylactic reaction

Anaphylactic shock

Anaphylactoid reaction

Anaphylactoid shock

Angioedema

Circulatory collapse

Circumoral oedema

Conjunctival oedema

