Corneal oedema

Cytokine release syndrome

Dialysis membrane reaction

Distributive shock

Drug hypersensitivity

Epiglottic oedema

Eye oedema

Eye swelling

Eyelid oedema

Face oedema

Gingival oedema

Gingival swelling

Gleich's syndrome

Hypersensitivity

Idiopathic urticaria

Infusion related reaction

Kounis syndrome

Laryngeal oedema

Laryngotracheal oedema

Limbal swelling

Lip oedema

Lip swelling

Oculorespiratory syndrome

Oedema mouth

Oropharyngeal swelling

Palatal oedema

AESI**Preferred Term**

	Periorbital oedema
	Pharyngeal oedema
	Scleral oedema
	Shock
	Swelling face
	Swollen tongue
	Tongue oedema
	Tracheal oedema
	Type 1 hypersensitivity
	Urticaria
	Urticaria cholinergic
	Urticaria chronic
	Urticaria popular
Renal toxicity: Nephrotoxicity	Acute renal failure
	Aminoaciduria
	Chronic renal failure
	Cylindruria
	Decrease in glomerular filtration rate
	Enzymuria
	Fanconi syndrome
	Glycosuria
	Increased serum creatinine
	Phosphaturia
	Proteinuria
	Renal dysfunction
	Tubular acidosis
	Tubulointerstitial nephritis
Renal toxicity: Urotoxicity	Hemorrhagic cystitis
	Hematuria
	RBC in urine

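### The SAP's infusion-related reaction (IRR) category is a 48-term list with no link to an infusion and no case review, so the reported IRR rate can include events that no infusion caused

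*SAP*

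**What the plan says.** **SAP.** Section 5.8.3 lists the AESI categories, "infusion-related reactions (IRR), cardiac arrhythmias, cardiac dysfunction, encephalopathy, renal toxicity. PT for AESI are listed in" Appendix 1. The IRR block of that appendix contains the term for an infusion related reaction itself and many broader ones, such as "Circulatory collapse" and "Urticaria chronic". The AESI summary is limited to treatment-emergent events: those starting or worsening from first dose to the 30-day follow-up visit, or at any time if serious and related. Section 5.8.3 repeats the TEAE and SAE summaries for treatment-related events, with relatedness recorded as a single yes or no for study treatment. It does not name the AESI summary in that repeat.

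**Protocol.** Two sections bear on what an IRR is.

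- Section 7.8.1: "Olaratumab infusion reactions will be defined according to the NCI-CTCAE Version 4.0 definition of IRRs". Symptoms arising during or after an infusion "may also be defined according to AE categories such as allergic reaction, anaphylaxis, or cytokine release syndrome". Investigators are encouraged to use the infusion-reaction term and to add "any additional terms (including those not listed here) that best describe the event".
- Section 9.2.3 includes infusion-related reactions among the AESI and says of AESI in general: "Each event is defined by a careful assessment and grouping of individual related Medical Dictionary for Regulatory Activities (MedDRA) preferred terms".

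Section 7.2.2.1 excludes infusion-related reactions from the DLTs.

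**The concern.** A term list finds candidate cases. It does not establish that an event was a reaction to an infusion. Several terms in the IRR block describe conditions with many causes (Shock, Circulatory collapse, Hypersensitivity, Urticaria), and one points to a different procedure altogether (Dialysis membrane reaction). With no condition on timing or review, an event on any day of the treatment-emergent window enters the IRR row.

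The primary objective is to characterise safety. Because IRRs are excluded from the DLTs, the AESI table is their main planned summary. If that row mixes infusion reactions with unrelated hypersensitivity, the IRR rate carried forward to a later study of this combination describes something other than what its label says. The cohorts are small, so one or two misplaced patients would change the reported percentage visibly.

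**Working it through.** The documents state no IRR rate, so there is no figure to reproduce. The check compares the definitions and then shows what one misplaced patient does to the rate.

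**1. The rules side by side**

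| Source | What makes an event an IRR | Tied to an infusion? | Case assessment? |
|---|---|---|---|
| Protocol 7.8.1 | CTCAE v4.0 definition; other terms allowed for symptoms during or after infusion | Yes | Investigator's report |
| Protocol 9.2.3 | Assessment and grouping of preferred terms | Not stated | Yes, unspecified |
| SAP 5.8.3 and Appendix 1 | Any treatment-emergent event with a listed term | No | None stated |

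**2. The list.** Counting the IRR block of SAP Appendix 1 gives 48 preferred terms. One is the infusion-related-reaction term itself; the other 47 can be reported for events with another cause.

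**3. Other causes that the protocol foresees**

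- Denosumab is a permitted concomitant drug. Section 7.8.6 notes its hypersensitivity risk and says not to give it within 3 days of olaratumab. A reaction to it, coded Hypersensitivity, Drug hypersensitivity or Urticaria, would enter the IRR row.
- Imaging is scheduled every 6 weeks during treatment (Table JGDR.2). Section 9.1.1 calls for intravenous and oral contrast unless contraindicated, and Table JGDR.1 anticipates serious contrast allergy. A contrast reaction would be counted in the same way.

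Neither is a reaction to a study-drug infusion. Nothing in SAP 5.8.3 removes them from the count.

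**4. Effect of one misplaced patient.** Group sizes are about 15 per cohort (protocol 5.1) and about 30 at the recommended regimen (protocol 5.2), the latter reported by the pooling in SAP 5.8. For a patient with no genuine IRR, the effect is 1/n:

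- n = 15: 1/15 = 6.7 percentage points; two patients, 2/15 = 13.3 points
- n = 30: 1/30 = 3.3 percentage points

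**5. Illustration under assumed rates.** Let q be the proportion of patients with an unrelated listed event and p the true IRR rate, taken as independent. Neither comes from the documents.

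Chance of at least one unrelated patient, 1 − (1 − q)^n:

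| q | n = 15 | n = 30 |
|---|---|---|
| 2% | 26% | 45% |
| 5% | 54% | 79% |
| 10% | 79% | 96% |

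Reported rate, 1 − (1 − p)(1 − q), at p = 10%:

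- q = 2%: 1 − 0.90 × 0.98 = 11.8%
- q = 5%: 1 − 0.90 × 0.95 = 14.5%
- q = 10%: 1 − 0.90 × 0.90 = 19.0%

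**The case against.** The strongest reply is that the protocol itself prescribes term grouping for AESI in section 9.2.3, and Appendix 1 is that grouping. A broad list also serves sensitivity, since section 7.8.1 invites investigators to describe a reaction with additional terms and a single-term count would miss reactions coded otherwise. Both arguments stand, and they are reasons to keep the list. They do not supply the assessment that 9.2.3 couples to the grouping.

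The SAP does offer partial mitigation. The infusion-related-reaction term appears on its own in the TEAE tables by preferred term, and the AESI cases are listed. But the single-term row is too narrow, the listing does not alter the count, and one relatedness question for all study treatment cannot identify olaratumab. No planned table gives a rate on the 7.8.1 definition.

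A reader might be tempted by stronger conclusions that the documents do not support:

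- *The SAP contradicts the protocol.* The protocol carries two approaches, and the SAP follows part of one.
- *Sepsis from a myelosuppressive backbone will be read as IRRs.* Febrile neutropenia, sepsis and septic shock are not in Appendix 1. Such a case would enter only if coded to a less specific term such as Shock.
- *Every hypersensitivity reaction to chemotherapy is misclassified.* The AESI are defined for the whole combination, so an infusion reaction to doxorubicin or ifosfamide is in scope.
- *Events count at any time, including long stretches without an infusion.* The summary is restricted to treatment-emergent events, and monotherapy still doses on Days 1 and 8 of each cycle.
- *Most counted events must lie away from an infusion, because few days are infusion days.* That assumes onset is independent of infusions, which is the very point in question.
- *The antibody tabulation will be mismatched.* Protocol 10.3.6 says "In the event of an IRR, the immunogenicity and olaratumab serum concentrations will be tabulated", but SAP 5.11 defers that work to a separate plan, and nothing says it uses the Appendix 1 list.

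**Conclusion.** The point holds as a defect in the stated counting rule. SAP 5.8.3 with Appendix 1 lets events with no connection to an infusion into the IRR rate, and specifies none of the assessment that protocol 9.2.3 calls for. The rate *can* be inflated; the documents do not show that it *will* be, or by how much. The only size that follows from the design is 6.7 percentage points per misplaced patient at n = 15, or 3.3 at n = 30, assuming that patient had no genuine IRR. The rates in the illustration rest on assumed p and q and on independence.

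The consequence is confined to the reported safety profile. IRRs are not DLTs, so no threshold in Table JGDR.7 depends on this count. The change is still worth making, because safety is the primary objective and the correction is nearly free.

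**What to change.** Amend SAP 5.8.3 as follows.

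1. **Main IRR count.** Patients with (a) an event the investigator reports as an infusion related reaction, or (b) any other Appendix 1 IRR term with onset in a prespecified window after a study-drug infusion, for example the infusion day or the day after. The documents give no window length, so the SAP should choose one and state why.
2. **Olaratumab shown separately.** Identify which qualifying events follow an olaratumab infusion. In combination cycles Day 1 also carries doxorubicin and ifosfamide, so timing alone will not always separate the drugs. Use clock times where recorded, and label the rest as following more than one drug.
3. **Second line.** Keep the unrestricted count, labelled as hypersensitivity or IRR terms regardless of timing.
4. **Protocol.** Reconcile 7.8.1 with 9.2.3 by saying which definition governs the reported IRR rate and what the assessment consists of. If medical review is preferred to a time window, name the reviewer's role and the criteria in advance.

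The cost is a few lines of SAP text and one date comparison. Infusion times are already recorded (protocol 7.1.1 and Appendix 4), and AE duration is already planned for the listings (protocol 10.3.2). The downside is that a late reaction not reported by the investigator as an IRR leaves the main count; the second line keeps it visible.

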5.8.4. Deaths, Other Serious Adverse Events

A summary of all deaths, including reasons for deaths, will be provided. All deaths, deaths on therapy, deaths within 30 days of discontinuation of study therapy, deaths on therapy or within 30 days of discontinuation of study therapy, and deaths after 30 days of discontinuation of study therapy will be summarized by reason for death. For deaths due to AE, the preferred term will be provided. In addition to the tabular summary, a by-patient listing of all deaths on study not attributed to study disease by the investigator will be provided.

5.8.5. Medical History Related to Infusion Related Reactions or Hypersensitivity

Summaries will be provided for prespecified medical history related to IRR or hypersensitivity for a patient and patient's first degree relatives.

5.8.6. Clinical Laboratory Evaluation

All relevant laboratory values will be graded according to CTCAE Version 4. Treatment-emergent changes will be summarized by the maximum postbaseline grade, and a shift table of baseline grade by maximum postbaseline grade will be produced. A listing will be provided with a flag for values outside of the laboratory normal range.

5.8.7. Vital Signs and Other Physical Findings

Actual values and changes from baseline for vital signs including temperature, blood pressure, respiratory and heart rate will be summarized by scheduled time point using descriptive statistics and listed. A summary of ECOG performance status at each scheduled time point will be provided.

5.8.8. Electrocardiograms, Echocardiogram / Multiple Gated Acquisition Scan

Electrocardiograms (ECG) findings that are considered to be a medical history condition or an AE will be summarized and listed.

Left ventricular ejection fraction (LVEF) results will be summarized by scheduled time point.

Changes in LVEF will also be summarized including percentage of patients with LVEF decrease of $\geq 10\%$ and below the lower limit of normal, or an absolute decrease of 20%, or an absolute LVEF decreases to or below 40%.

5.9. Efficacy Analyses

All efficacy analyses will be performed on the safety population to investigate antitumor activity within each cohort. This study is not designed to perform hypothesis testing on efficacy.

Response Evaluation Criteria In Solid Tumors (RECIST) version 1.1 will be applied as the primary criteria for assessment of tumor response. Local tumor imaging (investigator assessment with site radiological reading) will be used.

All time-to-event variables will be estimated using Kaplan-Meier method (Kaplan and Meier 1958) and summary statistics including median along with 95% CI as well as even-free rates (and 95% CI) at different time points will be presented.

5.9.1. Objective Response Rate and Disease Control Rate

Objective response rate (ORR) and disease control rate (DCR) are summary measures of best overall response (BOR) as defined by RECIST. BOR is derived from time point responses. All time point responses observed while on study treatment and during the short-term follow-up period (but before the initiation of postdiscontinuation therapy) will be included in the derivation. Best overall response of complete response (CR) and partial response (PR) should be confirmed by repeated assessment at least 4 weeks following the initial observation. Each patient's BOR will be categorized as CR, PR, stable disease (SD), PD, or not evaluable (NE). If appropriate, the best overall tumor response may be derived using all available lesion measurement data to confirm the investigator assessments.

ORR will be estimated by dividing the total number of responders (CR+PR) by the number of treated patients. DCR is defined as the number of patients with SD, confirmed PR or confirmed CR (CR+PR+SD) divided by the number of treated patients. The estimates of ORR and DCR will be reported with exact 95% confidence interval (CI) for each arm.

Individual changes in the tumor burden over time will be presented graphically by waterfall and spier plots within a tumor type.

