6.1. Inclusion Criteria

Patients are eligible to be included in the study only if they meet all of the following criteria:

- [1] Have a histological diagnosis of advanced STS (by local pathology review), for which treatment with doxorubicin, ifosfamide and mesna is deemed appropriate by the investigator. Patients with a diagnosis of Grade 1 liposarcoma (atypical lipomatous neoplasms) are eligible if there is histological or radiographic evidence of evolution to more aggressive disease.
- [2] Have measurable or nonmeasurable but evaluable disease as defined by the Response Evaluation Criteria in Solid Tumors (RECIST 1.1) (Eisenhauer et al. 2009). Tumors within a previously irradiated field will be designated as “nontarget” lesions unless progression is documented or a biopsy is obtained to confirm persistence at least 90 days following completion of radiotherapy.
- [3] Are ≥ 18 years of age at the time of consent.
- [4] Have given written informed consent prior to any study-specific procedures.
- [5] Have adequate hematologic, organ and coagulation function within 2 weeks (14 days) prior to enrollment:
 - Absolute neutrophil count (ANC) $\geq 1.5 \times 10^9/L$. Granulocyte-colony-stimulating factor (G-CSF) cannot be administered within 2 weeks (14 days) prior to enrollment.
 - Platelet count $\geq 100 \times 10^9/L$
 - Hemoglobin $\geq 9.0 \text{ g/dL}$. No transfusions are allowed within 2 weeks (14 days) prior to enrollment.
 - Serum creatinine ≤ 1.5 times upper limit of normal (ULN). If creatinine is above the ULN, the patient’s creatinine clearance must be $\geq 65 \text{ mL/min}$ (refer to [Appendix 6](#) for the Cockcroft-Gault formula for creatinine clearance).
 - Total bilirubin within ULN (except for patients with Gilbert’s syndrome, who must have a total bilirubin $< 3 \text{ mg/dL}$)
 - Alanine aminotransferase (ALT)/aspartate aminotransferase (AST) $\leq 3.0 \times \text{ULN}$; if the liver has tumor involvement, AST and ALT $\leq 5.0 \times \text{ULN}$ are acceptable

- An adequate coagulation function as defined by international normalized ratio (INR) $\leq 1.5 \times$ ULN or prothrombin time $\leq 1.5 \times$ ULN, and partial thromboplastin time $\leq 1.5 \times$ ULN (unless receiving anticoagulant therapy). Patients receiving warfarin are recommended to switch to low molecular weight heparin and should have achieved stable coagulation status prior to the first dose of study treatment.

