7.8.6. Other Concomitant Therapies

No other chemotherapy, radiotherapy, immunotherapy, cancer-related hormone therapy, or experimental drugs will be permitted while the patients are on this study. An exception will be made for:

- prostate cancer patients continuing GnRH agonist therapy or breast cancer patients continuing anti-estrogen therapy (for example, an aromatase inhibitor) as long as those

therapies have been installed for at least 3 months and are known to have been well tolerated

- bisphosphonate osteoclast inhibitors (for example, zoledronic acid or pamidronate) for treatment of bone metastases will be permitted while patients are on study treatment. The osteoclast inhibitor denosumab is also allowed. Denosumab is a monoclonal antibody and is associated with a risk of hypersensitivity reactions. Therefore, denosumab should not be administered within 3 days of olaratumab administration.
- palliative local treatment (for example, radiotherapy of ≤ 14 calendar days) in Cycles 2 and beyond following discussions between the investigators and the sponsor (for example, for pain control of a solitary [non-skull] skeletal metastasis) and written approval by the sponsor, as long as the patient has not developed another reason for study discontinuation.

[figure not shown]

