8.1. Discontinuation from Study Treatment

Patients will be discontinued from study treatment under the following circumstances:

- the patient is enrolled in any other clinical trial involving an investigational product or any other type of medical research judged not to be scientifically or medically compatible with this study
- the patient becomes pregnant during the study
- the patient is significantly noncompliant with study procedures and/or treatment
- the patient demonstrates disease progression
- the patient has unacceptable toxicity
- the patient, for any reason, requires treatment with another therapeutic agent that has been demonstrated to be effective for treatment of the study indication. Discontinuation from study treatment will occur prior to introduction of the new agent
- the patient undergoes surgical tumor resection
- the investigator decides that the patient should be discontinued from study treatment
- the patient requests to be discontinued from study treatment
- the patient's designee (for example, legal guardian or caregiver) requests that the patient be discontinued from study treatment

Patients who are discontinued from study treatment will have follow-up procedures performed as shown in the Schedule of Activities (Section 2).

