5.6.5. Poststudy Treatment Discontinuation Therapies

Therapies received following study treatment discontinuation will be summarized overall and by type of therapy.

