5.9.3. Duration of Response

The duration of response (DoR) time is defined only for responders (patients with a confirmed CR or PR). It is measured from the date of first evidence of CR or PR to the date of objective progression or the date of death due to any cause, whichever is earlier. For clarity, the start date should be determined by the initial assessment of CR or PR, not the date of confirmation of CR or PR. It is calculated as date of progression or death – date of first response evaluation of CR or PR + 1.

Duration of response (DoR) will be censored according to the same rules as PFS, with the addition of the following rule: if a patient begins postdiscontinuation therapy, DoR will be censored on the day of the last response evaluation prior to the initiation of postdiscontinuation therapy.

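### Best response and duration of response have no cut-off for palliative local treatment of a target lesion given during study treatment

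*SAP*

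**What the plan says.** **Best response.** SAP 5.9.1 derives best overall response from "All time point responses observed while on study treatment and during the short-term follow-up period (but before the initiation of postdiscontinuation therapy". Complete and partial responses need confirmation at least 4 weeks later. ORR and DCR are divided by all treated patients.

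**Duration of response.** SAP 5.9.3 applies the censoring rules for progression-free survival (PFS) and adds one: "if a patient begins postdiscontinuation therapy, DoR will be censored on the day of the last response evaluation" before that therapy starts.

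**What postdiscontinuation therapy covers.** SAP 5.6.5 places it after study treatment: "Therapies received following study treatment discontinuation will be summarized overall and by type of therapy". Protocol 10.3.3.4 agrees and names surgery, radiotherapy and systemic therapy as its types.

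**What is allowed on study treatment.** Protocol 7.8.6 makes an exception for "palliative local treatment (for example, radiotherapy of" at most 14 calendar days) "in Cycles 2 and beyond following discussions between the investigators and the sponsor". The illustration and remaining conditions are "for pain control of a solitary [non-skull] skeletal metastasis) and written approval by the sponsor, as long as the patient has not developed another reason" to discontinue.

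**Irradiated lesions at entry.** Inclusion criterion 2 in Protocol 6.1 says: "Tumors within a previously irradiated field will be designated as" nontarget, unless progression is documented or a biopsy at least 90 days after radiotherapy confirms persistence.

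**The concern.** SAP 4.2 states the efficacy objective as documenting antitumour activity of olaratumab with the chemotherapy backbone. The SAP protects that aim against therapy given after study treatment stops, but not against local anticancer treatment given earlier, while the patient is still on study drug. A target lesion that shrinks because it was irradiated would then count towards a response to the regimen. Irradiating a regrowing target lesion before progression is declared could also lengthen DoR.

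The study is open label, responses are assessed by the investigator, and cohorts are about 15 patients, so one misattributed response would be visible in the reported ORR. If no rule is set in advance, such a patient would have to be handled by a case-by-case decision made with the outcome known.

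**Working it through.** The plan gives no figure for this point: no target ORR and no expected rate of on-study radiotherapy. The check is therefore mainly of the text, with illustrative arithmetic.

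**Step 1. Does any rule remove the assessment?**

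| Provision | Covers local treatment on study drug? |
|---|---|
| SAP 5.9.1 therapy cut-off | No. It starts with postdiscontinuation therapy |
| SAP 5.9.3 extra DoR censor | No. Same trigger |
| SAP Table JGDR.5.1, seven PFS rules (also used for DoR) | No. None mentions radiotherapy, local treatment or new anticancer therapy |
| SAP 5.9.1 confirmation at 4 weeks or more | No. A lesion that stays small is confirmed at the next 6-weekly scan |
| SAP 5.9.1 not-evaluable category | Available, but nothing assigns it to a lesion treated on study |
| Protocol 6.1, criterion 2 | No. It concerns radiotherapy before entry |
| Protocol 8.1, "the patient undergoes surgical tumor resection" | Closes the surgical case, because resection ends study treatment. It does not reach radiotherapy |

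**Step 2. Can this produce a response?** Assume two target lesions of 40 mm, one irradiated and reduced to 15 mm, the other unchanged.

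- Sum before: 40 + 40 = 80 mm. Sum after: 15 + 40 = 55 mm.
- Change: (55 − 80)/80 = −31.25%.

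The documents cite RECIST 1.1 without restating its threshold for partial response. The example qualifies under any threshold up to 31.25%. If the threshold is taken as 30% (an assumption), the sum must fall by 0.30 × 80 = 24 mm. The irradiated lesion alone must then shrink by 24/40 = 60%. The case is possible but not easy to reach.

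**Step 3. Effect on DCR.** In the same example, without the radiotherapy effect both lesions are unchanged, which is stable disease and already counts in DCR. Scans are due every 6 weeks and progression ends study treatment, so most patients irradiated after the first scan will already have stable disease or better. A change in DCR is plausible mainly when local treatment comes in Cycle 2, before the first scan.

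**Step 4. Size for ORR.** The shift per patient is at most 1/n, reached only if that patient would otherwise be a non-responder.

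| Misattributed responders | n = 15 | n = 30 |
|---|---|---|
| 0 | 0 | 0 |
| 1 | 1/15 = 6.7 points | 1/30 = 3.3 points |
| 2 | 2/15 = 13.3 points | 2/30 = 6.7 points |

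SAP 5.9 reports efficacy by cohort, so 15 is the direct denominator. Thirty is the protocol's goal for the recommended regimen and applies if efficacy is pooled as SAP 5.8 pools safety.

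With assumed responder counts and exact 95% intervals, reclassifying one patient gives:

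- n = 15: 5/15 = 33.3% (11.8 to 61.6) becomes 4/15 = 26.7% (7.8 to 55.1).
- n = 30: 9/30 = 30.0% (14.7 to 49.4) becomes 8/30 = 26.7% (12.3 to 45.9).

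The shift is small beside the width of either interval.

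**The case against.** **The exception is tightly controlled.** Written sponsor approval is required, and the example is pain control of one bone lesion, which may well not be a target lesion. This stands as a reason to expect few cases. It sets no analysis rule, and the example does not restrict treatment to nontarget lesions.

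**RECIST and the investigator decide evaluability.** A reader could call the treated lesion not evaluable, and the SAP provides that category. This stands in part: a misattributed response is possible, not certain. But the plan does not require that call, and SAP 5.9.1 allows best response to be re-derived from all available lesion measurements with no exclusion.

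**The SAP does not abandon a protocol principle.** A reader might infer from criterion 2 that irradiated tumours can never be target lesions and that the SAP drops this after baseline. The documents do not support that. Criterion 2 has two exceptions, concerns radiotherapy before entry, and is not stated as an analysis rule.

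**A cut-off has its own cost.** It discards later assessments in untreated lesions, where a true drug response may appear, and censoring DoR at palliative treatment may be informative. This stands, and is why the present rule should be kept as a sensitivity analysis.

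**Nothing hangs on ORR.** SAP 5.9 says the study is not designed for efficacy testing, and dose progression rests on dose-limiting toxicities and safety. This stands and limits the priority of the point.

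**Conclusion.** The gap is real but small. As written, a response produced by local treatment of a target lesion during study treatment can enter ORR and DoR as a response to the regimen. The effect is at most 6.7 points of ORR per such patient in a cohort of 15, or 3.3 points in 30, and zero if only nontarget lesions are treated. Those maxima assume that the patient is a confirmed responder solely because of the local treatment.

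Two stronger conclusions might be drawn and are not supported. One is that DCR is inflated to a similar degree; the patient would usually have stable disease either way. The other is an expected bias of several points across the trial; the documents give no frequency of on-study local treatment, so any rate would be a guess, and the controls in Protocol 7.8.6 suggest it is low.

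PFS lies outside this point. Its rules cut off at no other therapy at all, which is a separate choice. The primary safety objective, the sample size and the dose-progression rules are unaffected.

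**What to change.** In SAP 5.9.1, state that if a target lesion receives local treatment on study, best overall response is derived only from assessments before that treatment. In SAP 5.9.3, state that DoR is then censored at the last adequate assessment before it. Say explicitly that local treatment of nontarget lesions alone changes neither rule. List the affected patients, and give their results under the present all-assessments rule as a sensitivity analysis. This extends the logic the SAP already applies to postdiscontinuation therapy and leaves patient management as it is.

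The drafting cost is two SAP sentences and a listing. The sponsor should also check that the treated site is recorded and can be matched to target-lesion identifiers. SAP 5.7 describes concomitant medications, and no section shows that this link exists, although the written approvals should identify the patients.

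The statistical cost is a few dropped assessments, some of which may hold true drug responses in untreated lesions, so ORR may be slightly lower. A patient treated before the first scan would have no usable post-baseline assessment and would count as a non-responder among all treated patients. A response seen before local treatment but not yet confirmed would also be lost from the main estimate. The sensitivity analysis shows both cases.
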